6.5.5 Dose Modifications for Avelumab as Single Agent

For avelumab, no dose reductions are permitted in this study, but doses may be omitted based on persisting toxicity. Any adverse event suspected to be immune related should be managed according to the guidance for management of irAEs (see the following tables).

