6.5.6 Adverse Drug Reaction Requiring Avelumab Discontinuation or Delays

The following adverse reactions (ADRs) require permanent treatment discontinuation of avelumab:

Any Grade 4 ADRs require avelumab treatment discontinuation except for single laboratory values out of normal range that are unlikely related to trial treatment as assessed by the Investigator(s), do not have any clinical correlate, and resolve within 7 days with adequate medical management.

Any Grade 3 ADRs require avelumab treatment discontinuation except for any of the following:

- Transient (≤ 6 hours) Grade 3 flu-like symptoms or fever, which is controlled with medical management
- Transient (≤ 24 hours) Grade 3 fatigue, local reactions, headache, nausea, or emesis that resolves to Grade ≤ 1
- Single laboratory values out of normal range (excluding Grade ≥ 3 liver function test increase) that are unlikely related to trial treatment according to the Investigator(s), do not have any clinical correlate, and resolve to Grade ≤ 1 within 7 days with adequate medical management
- Tumor flare phenomenon defined as local pain, irritation, or rash localized at sites of known or suspected tumor
- Change in Eastern Cooperative Oncology Group Performance Status (ECOG PS) to 3 that resolve to ≤ 2 within 14 days (infusions should not be given on the following cycle, if the ECOG PS is 3 on the day of trial drug administration).

Any Grade 2 ADR should be managed as follows:

- If a Grade 2 ADR resolves to Grade ≤ 1 within 2 weeks treatment may continue.
- If a Grade 2 ADR does not resolve to Grade ≤ 1 within 2 weeks, avelumab should be held. If after another 2 weeks the event has not resolved to Grade 1, the patient should permanently discontinue treatment with an avelumab (except for hormone insufficiencies, that can be managed by replacement therapy; for these hormone insufficiencies, up to 2 subsequent doses may be omitted).
- Upon the second occurrence of the same Grade 2 ADR (except for hormone insufficiencies that can be managed by replacement therapy) in the same patient, treatment with avelumab has to be permanently discontinued.

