6.5.8 Avelumab: Immune-Related Adverse Events

Because inhibition of PD-L1 stimulates the immune system, avelumab may cause toxicity by increasing the immune response, leading to inflammatory reactions collectively referred to as immune-related adverse events (irAEs).

Immune-related adverse events described with this class of drugs include drugs include dermatitis, pneumonitis, colitis, hepatitis, endocrinopathies including thyroid disorders (hyperthyroidism, hypothyroidism, thyroiditis), adrenal insufficiency, hypophysitis, and diabetes mellitus or hyperglycemia, rash, nephritis and renal dysfunction, encephalitis, eye disorders (including uveitis, iritis), and other immune-mediated reactions including myositis and myocarditis.

Any adverse event which may have an underlying immune-mediated mechanism including those described above, and without other confirmed etiologies, should be considered immune-related and managed according to guidelines described in this section.

Treatment of irAEs is mainly dependent upon severity (NCI CTCAE grade):

- Grades 1 to 2: treat symptomatically or with moderate dose steroids, more frequent monitoring.
- Grades 1 to 2 (persistent): manage similar to high grade AE (Grades 3 to 4).
- Grades 3 to 4: treat with high dose corticosteroids.

For patients receiving avelumab alone, any event suspected to be immune-related should be managed according to the guidance for management of irAEs in this section and Table.

| Gastrointestinal irAEs | | |
|------------------------------------------------------------------------------------------------------------------------------------------------------------------------------------------------------------------------------------------------------------------------------------|----------------------------------------------------------------------------------------------------------------------------------------------------------------------------------------------------------------------------------------------------------|-----------------------------------------------------------------------------------------------------------------------------------------------------------------------------------------------------------------------------------------------------------------------------------------------------------------------------------------------------------------------|
| Severity of Diarrhea/Colitis (NCI-CTCAE v4) | Initial Management | Follow-up Management |

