| Grade 1 Diarrhea: <4 stools/day over Baseline Colitis: asymptomatic | Continue avelumab therapy Symptomatic treatment (e.g. loperamide) | Close monitoring for worsening symptoms Educate subject to report worsening immediately If worsens: Treat as Grade 2, 3 or 4. |
| Grade 2 Diarrhea: 4 to 6 stools per day over Baseline; IV fluids indicated <24 hours; not interfering with ADL Colitis: abdominal pain; blood in stool | Withhold avelumab therapy Symptomatic treatment | If improves to Grade I : Resume avelumab therapy If persists >5-7 days or recurs: Treat as Grade 3 or 4. |
| Grade 3 to 4 Diarrhea (Grade 3): ≥7 stools per day over Baseline; incontinence; IV fluids 24 h; interfering with ADL Colitis (Grade 3): severe abdominal pain, medical intervention indicated, peritoneal signs Grade 4: life-threatening, perforation | Withhold avelumab for Grade 3. Permanently discontinue for Grade 4 or recurrent Grade 3. 1.0 to 2.0 mg/kg/day prednisone IV or equivalent Add prophylactic antibiotics for opportunistic infections Consider lower endoscopy | If improves: Continue steroids until Grade ≤ 1, then taper over at least 1 month; resume avelumab therapy following steroids taper (for initial Grade 3). If worsens, persists >3 to 5 days, or recurs after improvement: Add infliximab 5mg/kg (if no contraindication). Note: infliximab should not be used in cases of perforation or sepsis. |
| Dermatological irAEs | | |
| Grade of Rash (NCI-CTCAE v4) | Initial Management | Follow-up Management |
| Grade 1 to 2 Covering ≤30% body surface area | Continue avelumab therapy Symptomatic therapy (for example, antihistamines, topical steroids) | If persists >1 to 2 weeks or recurs: Withhold avelumab therapy |

| | | 
Consider skin biopsy
 
Consider 0.5-1.0 mg/kg/day prednisone or equivalent. Once improving, taper steroids over at least 1 month, consider prophylactic antibiotics for opportunistic infections, and resume avelumab therapy following steroids taper.
 
If worsens: Treat as Grade 3 to 4.
 |

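### Section 6.5.6 stops avelumab permanently after nearly any Grade 3 or 4 reaction, while the 6.5.8 irAE tables resume it in five graded entries, and no text says which section prevails

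*Protocol*

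**What the plan says.** Protocol section 6.5.6 sets out which adverse drug reactions (ADRs) end avelumab for good.

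- **Grade 4:** "Any Grade 4 ADRs require avelumab treatment discontinuation except for single laboratory values out of normal range". The exempt values must be judged unlikely to come from treatment, be clinically silent and clear within 7 days.
- **Grade 3:** "Any Grade 3 ADRs require avelumab treatment discontinuation except for any of the following". The five exceptions are brief flu-like symptoms or fever; brief fatigue, local reaction, headache, nausea or emesis; isolated laboratory values unlikely to come from treatment (liver tests not included); tumor flare; and a temporary fall to ECOG 3.
- **Grade 2:** a reaction that has not settled in 2 weeks is held. "If after another 2 weeks the event has not resolved to Grade 1, the patient should permanently discontinue treatment". "Upon the second occurrence of the same Grade 2 ADR", avelumab also ends for good. Both Grade 2 stops spare hormone insufficiencies that replacement can manage.

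The Grade 3 and Grade 4 rules spare no irAE, and 6.5.6 does not refer to 6.5.8.

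The tables in 6.5.8 work by organ and grade. For Grade 3 to 4 diarrhea or colitis the instruction is "Withhold avelumab for Grade 3. Permanently discontinue for Grade 4 or recurrent Grade 3", with avelumab resumed after the steroid taper for an initial Grade 3. For Grade 1 to 2 rash it is "If persists >1 to 2 weeks or recurs: Withhold avelumab therapy", again with resumption after the taper.

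Two sentences direct irAEs to these tables. Section 6.5.5 says "Any adverse event suspected to be immune related should be managed according to the guidance for management of irAEs". Section 6.5.8 says that an event with a possible immune mechanism and no other confirmed cause "should be considered immune-related and managed according to guidelines described in this section".

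**The concern.** An irAE caused by avelumab is also an ADR of avelumab, so both sections apply to it on their face. Where they give different instructions, the protocol tells the investigator both to end the drug permanently and to restart it after recovery.

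Re-challenge after a severe immune reaction is a direct safety decision. Permanent discontinuation gives up the rest of a course that may run to 2 years (section 7.5). With conflicting text, patients with the same event may be handled differently, and the same decision could be called compliant or a deviation depending on which section is cited.

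**Working it through.** There is no figure to reproduce. The check sets each graded 6.5.8 entry beside the 6.5.6 rule for the same grade.

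**Step 1: does 6.5.6 reach irAEs?** Its rules cover any ADR at the stated grade, and nothing narrows the term to non-immune reactions. The Grade 2 rules also exempt manageable hormone insufficiencies. That exemption would have little purpose if endocrine events of the immune type were outside the section.

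**Step 2: Grade 3 and 4 entries that resume avelumab.**

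| Event in 6.5.8 | Under 6.5.6 | Under 6.5.8 |
|---|---|---|
| Diarrhea/colitis, initial Grade 3 | Permanent stop | Withhold, taper, resume |
| Rash, initial Grade 3 | Permanent stop | Withhold, taper, resume |
| Creatinine increase, Grade 3 (row covers Grade 2 to 3) | Permanent stop | Withhold, taper, resume |
| Endocrinopathy, Grade 3 or 4 | Permanent stop | Withhold, resume at Grade 1 or below |
| Other irAE, first Grade 3 (row also covers Grade 2) | Permanent stop | Withhold, taper, resume |

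The 6.5.6 exceptions do not rescue these rows. In particular, the laboratory exception covers only values unlikely to be caused by treatment, so it cannot cover a creatinine rise attributed to avelumab. Count: five entries conflict at Grade 3, and one of the five (endocrine) also conflicts at Grade 4.

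**Step 3: Grade 2.** The differences include:

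- *Time limit, other irAEs.* 6.5.6 stops permanently at 2 + 2 = 4 weeks if the event is unresolved. The table sets the limit for a persistent Grade 2 or 3 irAE at 12 weeks, a difference of 12 − 4 = 8 weeks. This takes the persistence line of the table as sharing the permanent-stop instruction beside it.
- *Renal.* The Grade 2 to 3 row resumes after a taper of at least 1 month and has no 4-week stop of its own.
- *Rash recurrence.* 6.5.6 stops on a second occurrence of the same Grade 2 reaction. The rash row withholds on recurrence and then resumes.
- *Colitis recurrence.* The Grade 2 row sends a recurrence to the Grade 3 or 4 pathway, which can still end in resumption.

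**Step 4: where the sections agree.** Both stop permanently for Grade 3 to 4 pneumonitis and hepatic events, and for Grade 4 colitis, rash, creatinine increase and other irAEs. Recurrent Grade 3 colitis, rash and other irAEs also agree. Section 6.5.7 withdraws avelumab for Grade 3 or 4 infusion-related reactions, which is consistent with 6.5.6.

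**Step 5: is there a tie-breaker?** Sections 6.5.5 and 6.5.8 point to the tables, but neither disapplies 6.5.6. Section 7.5 lists unacceptable toxicity as a reason to leave treatment without saying which section defines it.

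**The case against.** The best reply is that the protocol already resolves this. Section 6.5.5, placed directly before 6.5.6, sends suspected irAEs to the tables, and 6.5.8 repeats the direction in broad terms. A general rule followed by event-specific tables is usually read with the specific text governing. On that view 6.5.6 covers the remaining, non-immune reactions, and only a cross-reference is missing. The hormone exemption shows that the Grade 2 rules had endocrine events in view; it does not show that 6.5.6 was meant to override the tables at Grade 3 and 4.

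Much of this stands. The tables are the more natural authority, and that lowers the seriousness of the point. It does not remove it. The routing sentences say how irAEs should be managed; 6.5.6 says what any Grade 3 or 4 reaction requires; no sentence ranks the two. A cautious investigator who stops permanently is following the text as faithfully as one who re-challenges.

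Three stronger readings are tempting and not supported:

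- A reader might infer a loss of exposure measured in doses. Any such figure needs an arbitrary time of onset and treatment to the full 2 years, and the protocol gives no frequency for these events.
- A reader might add hypophysitis as a sixth conflict. Its row describes symptoms by severity words and gives no CTCAE grade, so it conflicts only if severe or life-threatening is taken to mean Grade 3 to 4.
- A reader might infer that the trial's statistical conclusions are at risk. Under section 8.1 the analysis population is patients who complete TACE, whether or not avelumab continues, and neither the sample size nor the two-stage decision rule rests on the rule for stopping the drug.

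**Conclusion.** The conflict is real and should be corrected. Five graded 6.5.8 entries resume avelumab where 6.5.6 ends it at Grade 3, one of them also at Grade 4. The Grade 2 rules differ on persistence (4 against 12 weeks for other irAEs, and the renal row) and on recurrence (rash, colitis); these Grade 2 items are examples, not a complete count.

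The finding rests on two readings of the text: that an avelumab irAE is an ADR within 6.5.6, and that the routing sentences favor the tables without overriding 6.5.6. Its weight is in patient safety and uniform treatment. How many patients it would affect cannot be estimated from the protocol. Sample size, error rates and the primary analysis are unaffected.

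**What to change.** Add one sentence at the head of 6.5.6, covering all grades: *Suspected or confirmed irAEs are managed according to 6.5.8, which takes precedence over this section; infusion-related reactions follow 6.5.7; the rules below apply to all other ADRs.*

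Covering all grades matters, because an exception confined to the Grade 3 and 4 rules would leave the Grade 2 differences in place. The sponsor should accept knowingly that the stop on a second Grade 2 occurrence would then no longer govern irAEs; the tables' own recurrence instructions would.

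Two other repairs are less sound. Changing the five table entries to permanent discontinuation would, in the renal and other-irAE rows, end avelumab at a first Grade 2 event, which even 6.5.6 does not require. Adding a permanent stop for a second Grade 2 rash would make that event stricter than a first Grade 3 rash and go against the routing to the tables.

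The cost is a short protocol amendment. Data collection and analysis do not change.

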6.5.7 Management of Avelumab Infusion-Related Reaction

Since avelumab is administered IV, infusion-related reactions may occur (with symptoms such as fever, chills, rigors, diaphoresis, and headache). Treatment of the infusion-related reaction

and modifications of avelumab infusion are mainly dependent upon severity, as indicated in Table.

Treatment Modification for Symptoms of Infusion-Related Reactions

| NCI-CTCAE Grade | Treatment Modification for Avelumab |
|----------------------------------------------------------------------------------------------------------------------------------------------------------------------------------------------------------------------------------------------------------------------------------------------------------------------------------------------------------------------------------------------------------------------------------------------------------------------------------------------------------------------------------------|---------------------------------------------------------------------------------------------------------------------------------------------------------------------------------------------------------------------|
| Grade 1 — mild Mild transient reaction; infusion interruption not indicated; intervention not indicated. | Decrease the avelumab infusion rate by 50% and monitor closely for any worsening. |
| Grade 2 — moderate Therapy or infusion interruption indicated but responds promptly to symptomatic treatment (for example, antihistamines, NSAIDs, narcotics, IV fluids); prophylactic medications indicated for 24 h. | Temporarily discontinue avelumab infusion. Resume infusion at 50% of previous rate once infusion-related reaction has resolved or decreased to at least Grade 1 in severity, and monitor closely for any worsening. |
| Grade 3 or Grade 4 — severe or life-threatening Grade 3: Prolonged (for example, not rapidly responsive to symptomatic medication and/or brief interruption of infusion); recurrence of symptoms following initial improvement; hospitalization indicated for clinical sequelae. Grade 4: Life-threatening consequences; urgent intervention indicated. | Stop avelumab infusion immediately and disconnect infusion tubing from the subject. Subjects have to be withdrawn immediately from study avelumab and must not receive any further avelumab treatment. |
| 
 - If avelumab infusion rate has been decreased by 50% or interrupted due to an infusion reaction, it must remain decreased for the next scheduled infusion. If no infusion reaction is observed in the next scheduled infusion, the infusion rate may be returned to baseline at the subsequent infusions based on Investigator(s)'s medical judgment. - If hypersensitivity reaction occurs, the subject must be treated according to the best available medical practice. | |

IV = intravenous; NCI-CTCAE = National Cancer Institute-Common Terminology Criteria for Adverse Event; NSAIDs = non-steroidal anti-inflammatory drugs.

Additional Modifications for Patients with Grade 2 Infusion-Related Reactions If, in the event of a Grade 2 infusion-related reaction that does not improve or worsens after

implementation of the modifications indicated in Table 6 (including reducing the infusion rate by 50%), the Investigator(s) may consider treatment with corticosteroids, and the infusion should not be resumed. At the next dose, the Investigator(s) may consider the addition of H2 blocker antihistamines (eg, famotidine or ranitidine), meperidine, or ibuprofen to the mandatory premedication. Prophylactic steroids are NOT permitted.

Severe Hypersensitivity Reactions If hypersensitivity reaction occurs, the patient must be treated according to the best available medical practice. A complete guideline for the emergency treatment of anaphylactic reactions according to the Working Group of the Resuscitation Council (United Kingdom) can be found at <https://www.resus.org.uk/pages/reaction.pdf>. Patients should be instructed to report any delayed reactions to the Investigator(s) immediately.

Symptoms include impaired airway, decreased oxygen saturation (<92%), confusion, lethargy, hypotension, pale or clammy skin, and cyanosis. These symptoms can be managed with epinephrine injection and dexamethasone. Patients should be placed on monitor immediately, and the intensive care unit (ICU) should be alerted for possible transfer if required.

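### Section 6.5.7 gives two rules for an avelumab infusion reaction that does not respond to interruption or worsens after restart: permanent withdrawal in the table, a possible further dose in the paragraph below it

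*Protocol*

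**What the plan says.** Protocol section 6.5.7 manages infusion reactions by grade in a table, followed by a paragraph of extra measures for Grade 2.

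- **Table, Grade 2 definition:** "Therapy or infusion interruption indicated but responds promptly to symptomatic treatment".
- **Table, Grade 2 action:** interrupt the infusion, then "Resume infusion at 50% of previous rate once infusion-related reaction has resolved or decreased to at least Grade 1 in severity".
- **Table, Grade 3 definition:** prolonged, for example "not rapidly responsive to symptomatic medication and/or brief interruption of infusion"; or "recurrence of symptoms following initial improvement".
- **Table, Grade 3 or 4 action:** "Subjects have to be withdrawn immediately from study avelumab and must not receive any further avelumab treatment".
- **Table note on later infusions:** after a reduction or interruption the next infusion stays at the reduced rate. "If no infusion reaction is observed in the next scheduled infusion, the infusion rate may be returned to baseline", subject to medical judgement.
- **Paragraph below the table:** it applies "in the event of a Grade 2 infusion-related reaction that does not improve or worsens after" the table's modifications, expressly including the halved rate. Corticosteroids may be considered and the infusion is not to be resumed. It continues: "At the next dose, the Investigator(s) may consider the addition of H2 blocker antihistamines", meperidine or ibuprofen. It does not mention withdrawal from avelumab.

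Section 6.5.6 adds two general rules. Grade 3 drug reactions end avelumab, with listed exceptions. A second occurrence of the same Grade 2 reaction also ends it. Section 6.6 has acute toxicities of Grade 3 or higher recorded on Form C.

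**The concern.** The paragraph keeps the Grade 2 label for a reaction that has failed the condition the table sets for Grade 2. The event it describes matches the table's Grade 3 wording, but the consequence is different: the table ends avelumab, while the paragraph stops one infusion and moves on to the next.

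At stake is re-exposure after a reaction that did not respond or came back. Two clinicians who both follow the protocol could act in opposite ways. If the next dose passes without a reaction, the table note even allows the full rate again.

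A lesser consequence concerns reporting. If the Grade 2 label is carried into the record, the event drops out of the acute Grade 3 or higher toxicity count in section 6.6.

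**Working it through.** The plan states no figure to reproduce. The check sets the two texts of section 6.5.7 side by side for each event the paragraph names.

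| Event | Grade and action under the table | Grade and action under the paragraph |
|---|---|---|
| (a) No improvement after interruption and treatment | Fails the prompt-response condition for Grade 2 and meets the non-response wording of Grade 3: no further avelumab | Grade 2: infusion not resumed, next dose foreseen |
| (b) Worsening after restart at half rate | Meets the recurrence wording of Grade 3: no further avelumab | Grade 2: infusion not resumed, next dose foreseen |
| (c) Residual Grade 1 symptoms that merely persist after a prompt response | Can stay Grade 2 | Grade 2: no conflict |

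**Step 1, event (a).** Interruption is the table's first Grade 2 action. A reaction that does not improve after it has not responded rapidly to a brief interruption, which is one of the table's own examples of Grade 3.

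**Step 2, event (b).** The table permits restart only once the reaction has resolved or fallen to Grade 1, so any restarted infusion follows an improvement. Symptoms that worsen again after restart are symptoms returning after initial improvement. The table asks for improvement, not full resolution, before a return counts as recurrence.

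**Step 3, doses after the event.** Under the Grade 3 row: 0. Under the paragraph: at least 1. Further doses follow only if the reaction does not recur, because section 6.5.6 ends avelumab at the second occurrence of the same Grade 2 reaction.

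**Step 4, effect on the toxicity count.** The shift per patient labelled Grade 2 instead of Grade 3 is 100/n percentage points. The values of n come from section 8.2.

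- n = 33 (target accrual): 100/33 = 3.0 points
- n = 29 (two-stage total): 100/29 = 3.4 points

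Neither n is the number of patients who receive avelumab, which the protocol does not give. If that number is smaller than 29, the shift per patient is larger than 3.4 points.

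**The case against.** The strongest reply is that the paragraph overrides nothing. Its heading limits it to Grade 2, and section 6.5.7 says that management depends mainly on severity. A site can grade by the table first, withdraw the patient if the event is Grade 3, and use the paragraph only while the event is truly Grade 2. The next-dose sentence is optional advice that could be read as covering any Grade 2 patient. This reading does not rescue the text. The paragraph's stated trigger is failure to improve, or worsening, after the table's steps, and once those events are graded by the table almost nothing is left for it to govern.

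A second reply concerns event (b). Restart is allowed with residual Grade 1 symptoms, and residual symptoms that intensify again may not be recurrence in the clinical sense. There is some room for judgement here, but the table's wording requires only initial improvement, which restart presupposes. Symptoms that merely persist at Grade 1 are outside the conflict.

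A third reply points to the safeguards: the halved rate at the next infusion, mandatory premedication, access to intensive care, 30 minutes of observation, and the second-occurrence rule in section 6.5.6. These stand. They reduce the risk of the next dose and limit later ones, but they do not prevent the first re-exposure.

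The reply also holds that the effect on the Grade 3 count is speculative, because section 7.7.6 has severity recorded by the CTC criteria whatever the management heading says. That is fair. The reporting effect is only a possibility, and the finding does not depend on it.

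**Conclusion.** Section 6.5.7 is wrong as written. For a reaction that does not respond to interruption, or that worsens after restart, the table ends avelumab while the paragraph below it labels the reaction Grade 2 and foresees another dose. The size is 0 further doses against at least 1, for each patient concerned. The possible effect on the Grade 3 or higher incidence is 3.0 to 3.4 percentage points per patient on the planned numbers.

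The conclusion assumes that the paragraph's reference to Table 6 means the table in the same section, which its mention of the halved rate supports. It also takes the 6.5.7 table as the specific rule for infusion reactions. Some Grade 3 exceptions in section 6.5.6, such as short-lived controlled fever, could cover certain infusion symptoms, but the table carries no exception.

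The primary analysis, the stopping rule and the special-interest status of infusion reactions are unaffected. The point should be fixed because it governs re-dosing after a safety event.

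**What to change.** Add to the paragraph on additional Grade 2 modifications in section 6.5.7: *A reaction that meets the Grade 3 criteria of the table (no rapid response to medication or to a brief interruption, or symptoms that return or worsen after initial improvement) is graded at its worst grade and follows the Grade 3 row: avelumab is permanently discontinued.*

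Then limit the next-dose premedication sentence to reactions that stayed at Grade 2 or below, including residual Grade 1 symptoms after a prompt response.

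This is a wording change with no extra visits, tests or patients. The cost is that a few patients may stop avelumab earlier than under the present paragraph, which the table already requires.
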